7. ETHICS AND INFORMED CONSENT

7.1 Regulation statement

This study will be conducted according to the principles of the Declaration of Helsinki (revision Fortaleza, Brazil, October 2013). Approval to carry out this study will be sought from the relevant National and local Ethical Review Boards, as mandated by the country legislation. Ethical review will be requested from the Oxford Tropical Research Ethics Committee (OxTREC) and from relevant National Ethics bodies and Institutional review boards, as mandated by national and site regulations.

7.2 Recruitment and consent

Family members and primary caregivers will be invited to participate in the study and written consent obtained. If eligibility is confirmed, the study will be explained to the patient or patient relative/legal guardian, including detailed explanation of the participant information sheet and informed consent form.

7.3 Benefits and risks assessment

The participation in this observational study will not bring direct benefits to the patient or family. However the findings of the OOPE study will provide important information for policymakers on the burden of OOPE/CHE and potential solutions. No safety concerns are envisaged for this observational study based on information collected from patients or caregivers, with no influence on patient treatment or procedures.

8. FUNDING

The study will be supported by the Wellcome award, Collaboration for Research, Implementation and Training in Critical Care in Asia and Africa (Grant number: 224048/Z/21/Z).

10. APPENDIX

Appendix 1. Operational definitions

Term	Definition
OOPE	Defined as the cost incurred by individuals or households at the time of receiving any healthcare services in the ICU, including the component of cost-sharing (the part not covered by a third party like, an insurer) and informal payments (e.g., tips and under-the-table payments), but excluding insurance premiums and any reimbursements from the third-party payers (e.g., the government, a health insurance fund or a private insurance company). OOPE includes direct medical and direct non-medical costs, but excludes indirect costs (such as income/productivity loss).
Catastrophic health expenditure (CHE):	For CHE incidence estimation, there is no single agreed threshold. In this study CHE will be defined as OOPEs exceeding 10% of the household budget (yearly income or consumption expenditure). In sensitivity analysis, we will apply the higher threshold level of 25%.
Direct costs	Direct costs are expressed as expenditure during ICU treatment by households and consist of two main categories: direct medical cost and direct non-medical cost.
Direct medical costs	Subcategory of 'direct costs' referring to direct payments made by individuals to healthcare providers at the time of service use. These include those costs that are consumed for healthcare resources during ICU care and will be classified across 7 categories. 
 - Facility/provider fees, e.g. ICU bed charges, hospital daily rates, theater fees. - Laboratory costs - Medication costs e.g. drugs, fluids, nutrition solutions, bandages - Procedure costs e.g. diagnostic imaging procedures, mechanical ventilation, dialysis - Consumables e.g. (ventilator circuits, infusion sets, ventilation masks, gloves, alcohol rub, etc.) - Medical nutrition - Other costs These exclude any prepayment for health services, for example in the form of taxes or specific insurance premiums or contributions and where possible, net of any reimbursement to the individual who made the payments.
Direct non-medical costs	Subcategory of 'direct costs' including transportation, lodging, food items, informal payments and tips, payments incurred by caregivers and family for helping the patients during treatment.
Yearly/ Annual Income	Annual income refers to the total amount of money earned by a household over the course of a year (i.e. last 12 months preceding this survey time). This income can come from various sources, such as salary or wages from employment, profits from a business, rental income, investment income, land, or any other source of income received over the course of a year.
Yearly/ Annual Expenditure	Annual expenditure refers to the total amount of money spent by a household over the course of a year (i.e., last 12 months preceding this survey). This includes all expenses such as rent or mortgage payments, utilities, groceries,

	transportation costs, insurance, taxes, entertainment, food and any other expenses incurred during the year.
Family caregivers	
Defined as any family member, relative, partner or friend of the ICU patient, who were caring for the patient while he or she stayed in the ICU with or without remuneration.
 
- Primary family caregiver: is the family caregiver with the most patient contact.- Secondary family caregivers: defined as any other family member or friend over the age of 18 involved in patient care and listed along with their time commitment by the primary family care-giver.
Coping strategies	
Any mechanisms for OOPE coverage by patient or family member, including:
 
- Savings: own income.- Medical debt: defined as personal debt derived from healthcare expenditures or paying for medical OOPE by borrowing money from friends or family, institutional loans (banks, etc) or non institutional loans (borrowing from black market).- selling of personal property- limitation to procurement of medical services or drugs- other

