2.2 ICU costs

ICU admission is often unexpected, the treatment and interventions needed are usually unpredictable and length of stay frequently prolonged. In fact, a single ICU admission can cost from few hundreds to more than one hundred thousand US dollars.⁴ Thus ICU care often results in spiraling costs, which if not absorbed by welfare or insurance systems, directly fall on the patient and family. Costs can be classified as direct and indirect costs, with direct cost further divided in 'medical' and 'non-medical' domains. *Direct* medical costs include any daily fixed costs for the ICU bed, consumables (eg. medications, laboratory tests, nutrition, fluids, bandaging, ventilation circuits) which often fall at the pocket of patients and families. Studies assessing ICU direct costs are available from LMICs such as Brazil, Thailand, Vietnam and India.⁵⁻⁸ Direct non-medical costs include transportation and accommodation. In addition, *indirect costs* arise such as loss of income for patients, especially ones employed without sick leave cover. For families and caregivers, income loss and productivity loss are associated with time spent being at the hospital with their relatives.

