4.4 Study parameters/endpoints

Primary endpoints:

- Costs per complete patient episode, as actually spent in US dollars and International dollars (purchasing power parity exchange rate) in ventilated versus non-ventilated groups.
- Relative risk of CHE in ventilated versus non-ventilated groups.

Secondary endpoints:

- Risk factors for CHE (presumptive list in section 4.6)
- Frequency of different coping strategies for financial coverage of ICU costs

Tertiary endpoints

- Proportion of direct medical versus direct non-medical costs in the total OOPes
- Patient family socio-economic status (SES) or income
- Paying structures, models by country.

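### Appendix 1 gives nutritional feeds two cost categories and lists informal payments as non-medical against its own definition of direct medical costs

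*Protocol*

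**What the plan says.** Protocol section 4.6, part C, sends the reader to Appendix 1 for the cost categories and their operational definitions. The appendix divides direct medical costs into seven categories, and seven are listed. One is "Medication costs e.g. drugs, fluids, nutrition solutions, bandages". Another, with no examples and no stated boundary, is "Medical nutrition".

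The appendix describes direct medical costs as "referring to direct payments made by individuals to healthcare providers at the time of service use". The next row describes direct non-medical costs as "including transportation, lodging, food items, informal payments and tips", followed by what families and caregivers pay while helping the patient. The OOPE row counts informal payments, both gratuities and unofficial charges, among the costs met when ICU services are received.

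Two planned outputs use these categories. Section 4.8a, under the primary endpoint analysis, summarises direct medical costs by category and names medication and medical nutrition as separate items. Section 4.4 lists as a tertiary endpoint "Proportion of direct medical versus direct non-medical costs in the total OOPes".

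**The concern.** A cost classification is useful only if each purchase has one place. Here a feed has two, and an informal payment to a provider satisfies one definition while being named under the other.

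The study seeks at least 30 ICUs in at least 5 countries (section 4.3). Section 4.7 says that stakeholders added local examples to the categories and agreed definitions, but the protocol gives no precedence rule for an item that fits two headings. Differences between sites or countries in medication and nutrition spending could then be partly differences in coding. The medical/non-medical proportion would also carry a label that does not match the protocol's own definition of medical cost, which matters most where informal charging is common.

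An analysis plan may be unable to repair this later. The category is assigned when the cost form is completed, so unless the form keeps item detail, feeds booked under Medication cannot afterwards be separated from drugs.

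**Working it through.** The protocol has no figure to reproduce on this point. The check sets the definitions side by side and follows each ambiguity through to the outputs.

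**Step 1: feeds.** Let *M* be medication spending without feeds, *N* medical nutrition without the feed in question, and *f* the cost of that feed.

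| | Medication | Medical nutrition | Sum of the two |
|---|---|---|---|
| Site using the Medication example | *M* + *f* | *N* | *M* + *N* + *f* |
| Site using the separate category | *M* | *N* + *f* | *M* + *N* + *f* |

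Both codings are valid under Appendix 1. Each subtotal moves by *f*; the direct medical total does not move. On assumed values, if medication including feeds is 30% of OOPE and feeds are 2%, 5% or 10% of OOPE, the medication subtotal is 30% under one coding and 28%, 25% or 20% under the other. Medical nutrition gains the same 2, 5 or 10 points.

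**Step 2: informal payments.** Let *D* be formally paid direct medical costs, *s* informal payments made to providers, *R* all other non-medical costs, and *T* = *D* + *s* + *R* total OOPE.

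- Medical share following the listing: *D*/*T*.
- Medical share following the definition: (*D* + *s*)/*T*.
- Difference: *s*/*T*.

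The protocol gives neither *D*/*T* nor *s*/*T*. Assuming *D*/*T* = 75%:

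| *s*/*T* (assumed) | Share by listing | Share by definition |
|---|---|---|
| 1% | 75% | 76% |
| 5% | 75% | 80% |
| 10% | 75% | 85% |
| 15% | 75% | 90% |

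The table shows how far the endpoint depends on which sentence governs. It does not show that either column is the true value.

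**Step 3: primary endpoints.** CHE is *T* divided by yearly household income, exceeding 10% (section 4.8b). *T* contains both the medical and the non-medical part, and the OOPE row includes informal payments explicitly. Moving an item between categories leaves *T* unchanged, and therefore cost per episode, CHE status and the relative risk of CHE.

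**The case against.** The strongest reply concerns informal payments. They are named in the non-medical row and in none of the seven medical categories, and a specific listing normally governs a general description. A site following the list would code them one way, so the protocol does not by itself create site-to-site variation here. This largely stands. What remains is mainly a definitional inconsistency, with variation only if some sites apply the definition instead. It is also fair that the non-medical row names no recipient; that some of these payments go to providers is inferred from the OOPE row.

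On feeds, the reply is that both headings are direct medical, so only two descriptive subtotals are exposed. That is correct and sets the size of the point, but it does not remove the overlap.

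A reader might infer more, in four ways that the document does not support:

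- *That feeds will be entered twice, inflating OOPE and CHE.* Uncertainty about the heading is not an instruction to enter a purchase twice. Research assistants support data collection, and the cost form is not shown.
- *That bandages are also misclassified.* Section 2.2 speaks of "consumables (eg. medications, laboratory tests, nutrition, fluids, bandaging, ventilation circuits", but this is background prose that also calls medications and laboratory tests consumables. It is not a coding scheme, and Appendix 1 gives bandages one place.
- *That ventilation has two homes.* Appendix 1 has "Procedure costs e.g. diagnostic imaging procedures, mechanical ventilation, dialysis" and, under consumables, "ventilator circuits, infusion sets, ventilation masks, gloves, alcohol rub, etc". The procedure and the disposables are different purchases, each named once.
- *That the medical share will be biased by a known amount.* Any such figure rests on an assumed share of informal payments and on calling one of the two definitions true.

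**Conclusion.** The point holds as a minor defect of definition, in two parts. The overlap between nutrition solutions and medical nutrition is plain in Appendix 1 and can make two subtotals in section 4.8a non-comparable across sites. The conflict over informal payments leaves the tertiary medical/non-medical proportion at odds with the stated meaning of a direct medical cost, by as many percentage points as informal payments to providers contribute to OOPE.

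The protocol gives no data on either quantity, so the size is known only as a one-for-one relation. The conclusion assumes that the unseen cost form follows Appendix 1, as section 4.6 indicates, without finer instructions that settle these items. It also assumes that at least some informal payments go to providers. Total OOPE, CHE and the primary comparison are unaffected.

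**What to change.** 1. In Appendix 1, remove nutrition solutions from the Medication examples and state that all prescribed feeds are coded under medical nutrition.
2. Record informal payments on their own line of the cost form. Reconcile the direct medical definition with the place where they are listed, for example by a clause naming the exception. Report the medical/non-medical proportion with and without that line. A separate line does not require the recipient to be recorded.

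The cost is a few words in the appendix and the form, a short note to sites already trained on the categories, and one extra version of a descriptive endpoint. Data already entered can be recoded only where item detail was kept. Where it was not, the affected subtotals should be reported with that limitation stated. No extra patients or visits are needed.
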